5.1.1 Statistical Analysis Plan

5.1.2 Descriptive Statistics

All data will be validated according to appropriate rules based on their characteristics and then subjected to normal descriptive analyses (mean, median, mode, standard deviation, standard error of the mean, minimum and maximum values, interquartile range). Continuous variables with Gaussian distribution will be represented by mean \pm standard deviation, while non-Gaussian variables will be represented by median and interquartile range. Categorical variables will be described using tables of relative and absolute frequencies.

5.1.3 Primary Endpoint

Tutti i dati saranno validati con delle opportune regole in base alle loro caratteristiche, e quindi sottoposti alle normali analisi descrittive (media, mediana, moda, deviazione standard, errore standard della media, valore minimo e massimo, range interquartile). Le variabili continue distribuite in modo Gaussiano saranno rappresentate da media \pm deviazione standard, mentre quelle non

Gaussiane saranno rappresentate da mediana e range interquartile. Le variabili categoriche saranno descritte con tabelle di frequenza relativa ed assoluta.

The primary endpoint will be determined by the fraction of enrolled subjects who reduce the VAS scale value by at least 30% after 6 weeks (T6s) from the start of treatment. The percentage fraction will be calculated with its 95% confidence interval according to Clopper-Pearson.

5.1.4 Secondary Endpoints

The secondary endpoints will consist of evaluating the performance of MD-Small Joints Collagen Medical Device through:

- VAS at T3s and T16s/FU compared to T0;
- DASH at T6s and T16s/FU compared to T0;
- FIHOA at T6s and T16s/FU compared to T0;
- Pinch Strength Test at T6s and T16s/FU compared to T0: using repeated measures ANOVA within subjects, or with the Friedman test, depending on the distribution of the data.
- Consumption of analgesics in various stages of the study: through quantitative and qualitative counting of the drugs used.
- Incidence of Adverse Events: as incidence and incidence rate for each individual type of Adverse Event and cumulatively for all.

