The enrolled subject will be assigned a complex alphanumeric identification code. The collected data must be entered into the e-CRF within the following 48 hours.

T1 settimana (± 1 gg):

At one week from T0, the second intra/peri-articular infiltration of MD-Small Joints Collagen Medical Device will be performed (see § 4.12), and the use of the analgesic medication will be evaluated through the analysis of the clinical diary. Any adverse events occurring after the first administration will also be assessed.

T2 weeks (±1 day):

At two weeks from T0, the third intra/peri-articular infiltration of MD-Small Joints Collagen Medical Device will be performed (see § 4.12), and the use of the analgesic medication will be evaluated through the analysis of the clinical diary. Any adverse events occurring after the second administration will also be assessed.

T3 weeks (±1 day):

At three weeks from T0, the fourth peri-articular infiltration of MD-Small Joints Collagen Medical Device will be performed (see § 4.12), and the use of the analgesic medication will be evaluated through the analysis of the clinical diary. The evaluation of VAS will be conducted. Any adverse events occurring after the third administration will also be assessed. The collected data must be entered into the e-CRF within the subsequent 48 hours.

T4 weeks (±1 day):

At four weeks from T0, the fifth and final peri-articular infiltration of MD-Small Joints Collagen Medical Device will be performed (see § 4.12), and the use of the analgesic medication will be evaluated through the analysis of the clinical diary. Any adverse events occurring after the fourth administration will also be assessed.

6 weeks (±2 days):

At six weeks from T0, and two weeks after the end of infiltrations, the following evaluations will be performed:

- VAS assessment;
- DASH assessment;
- FIHOA assessment;
- Pinch Strength Test evaluation using dynamometer;
- evaluation of the use of analgesic medication through the analysis of the clinical diary;

assessment of any adverse events occurring after the fifth administration. The collected data must be entered into the e-CRF within the subsequent 48 hours.

T16 weeks/FU (±7 days):

At four months from enrollment, and twelve weeks after the end of infiltrations, the following evaluations will be performed again:

- VAS assessment;
- DASH assessment;
- FIHOA assessment;

- Pinch Strength Test evaluation using dynamometer;

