4.13.2 Secondary Endpoints

The secondary endpoints will include evaluating the performance of MD-Small Joints *Collagen Medical Device* through:

- VAS at T3s and T16s/FU compared to T0;
- DASH at T6s and T16s/FU compared to T0;
- FIHOA at T6s and T16s/FU compared to T0;
- Pinch Strength Test at T6s and T16s/FU compared to T0;
- Consumption of analgesics during various stages of the study;
- Incidence of Adverse Events.

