6.2 Amendments to the Clinical Investigation Plan

Qualsiasi modifica al presente Piano di Indagine sarà sottomessa dallo Sponsor, in forma di emendamento, ai Comitati Etici Territoriali di riferimento dei Centri Sperimentali per opportuna approvazione.

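### Section 5.1.4 words the scale-based secondary endpoints as eight visit-versus-T0 comparisons, but the method it fixes is an omnibus test across visits; the gap is firmest on the Friedman branch.

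*Protocol*

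**What the plan says.** Sections 4.13.2 and 5.1.4 list the same scale-based secondary endpoints, each tied to two visits: "VAS at T3s and T16s/FU compared to T0", "DASH at T6s and T16s/FU compared to T0", "FIHOA at T6s and T16s/FU compared to T0", and pinch strength at the same two visits as DASH and FIHOA. Four scales at two visits each make eight comparisons with T0.

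The method in 5.1.4 is "using repeated measures ANOVA within subjects, or with the Friedman test, depending on the distribution of the data". The clause follows the colon in the pinch strength item. Read literally, the other three scales have no inferential method. I take the more generous reading, that it covers all four.

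Two other places bear on the point. Section 5.1.2 says that all data will be "subjected to normal descriptive analyses (mean, median, mode, standard deviation, standard error of the mean, minimum and maximum values, interquartile range"), so T16 values will be seen beside T0 values. For the primary endpoint, 5.1.3 does fix an interval: "The percentage fraction will be calculated with its 95% confidence interval according to Clopper-Pearson". No T0 contrast, paired test or interval for a change is named for the secondary scales. Analgesic use and adverse events have their own summaries and are not part of this point.

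**The concern.** The endpoint and the method in the same item ask different questions. The endpoint asks how far a subject has moved from T0 by a given visit. Repeated-measures ANOVA, taken as its F test, and the Friedman test ask whether the visits differ at all. A significant answer to the second does not say which visit differs from T0, or by how much.

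This matters most at T16. The visit schedule in 4.9.2 places it "At four months from enrollment, and twelve weeks after the end of infiltrations" (the synopsis gives 10 weeks, a separate discrepancy). It is the only assessment after T6 and so the only evidence on durability. If benefit at T6 is real but lost by T16, the omnibus test can still be clearly significant.

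**Working it through.** **The plan's own figures.** Section 5.1 gives figures for the primary endpoint only, and they reproduce. With 33 subjects and p0 = 0.2, P(X ≥ 12) = 0.0216 and P(X ≤ 1) = 0.0059, together 0.0275 (stated 2.75%). Power at 0.5 is 0.9599 (stated 95.99%). 33/0.8 = 41.25, rounded up to 42. This point does not rest on them, except that n = 33 is borrowed below. No figure is stated for the secondary endpoints.

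**Assumptions, not in the protocol.** n = 33 complete subjects; normal data with equal SD at each visit (unit SD); equal correlation ρ between visits, 0.3 / 0.5 / 0.7; a fall of 0.5 SD at the early visit or visits; two-sided 5% tests.

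**Omnibus ANOVA, three visits (DASH, FIHOA, pinch strength).** Power follows the noncentral F distribution with λ = n·Σ(μ − mean μ)²/(1 − ρ), on 2 and 64 degrees of freedom.
- Benefit gone at T16, means (0, −0.5, 0): the sum of squares is 1/6.
- Benefit kept at T16, means (0, −0.5, −0.5): the sum of squares is again 1/6.
- In both cases λ = 33 × (1/6)/(1 − ρ) = 5.5/(1 − ρ) = 7.86 / 11.0 / 18.3.

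| Test, three visits | Gone at T16 | Kept at T16 |
|---|---|---|
| ANOVA, omnibus (exact) | 68.7 / 83.5 / 97.1% | 68.7 / 83.5 / 97.1% |
| Friedman (10,000 simulated trials) | 53.2 / 67.8 / 89.2% | 53.1 / 68.8 / 89.7% |
| T16−T0 paired t (exact) | 5% | 65.3 / 79.5 / 94.9% |
| T16−T0 Wilcoxon signed-rank (simulated) | 4.8 / 4.6 / 4.9% | 63.4 / 77.4 / 93.9% |

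The omnibus tests do not separate the two outcomes. The T0 contrast does.

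**VAS with all four visits (T0, T3, T6, T16).** Gone, means (0, −0.5, −0.5, 0): the sum of squares is 0.25 and ANOVA power 81.6 / 93.2 / 99.5%. Kept, means (0, −0.5, −0.5, −0.5): the sum of squares is 0.1875 and power 68.3 / 83.6 / 97.4%. The exact equality is special to three visits. With four, the omnibus test is significant more often when the benefit has vanished.

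**A different assumed effect.** With a fall of 0.75 SD at T6 only and no change at T16 (4,000 simulated trials per case, three and four visits), ANOVA is significant in 96–100%, Friedman in 88–100%, and the T16−T0 paired t test in 4.5–5.5%.

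**Precision of the change from T0.**
- Paired: t(0.975, 32)·√(2(1 − ρ)/33) = 2.037 × 0.206 / 0.174 / 0.135 = 0.42 / 0.35 / 0.27 SD.
- From the ANOVA residual mean square, which estimates 1 − ρ under these assumptions: t(0.975, 64)·√(2(1 − ρ)/33) = 1.998 × the same = 0.41 / 0.35 / 0.27 SD.

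The two agree closely, so the ANOVA branch contains the precision. The Friedman statistic is built on within-subject ranks and has no counterpart.

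**Multiplicity if eight contrasts are tested.** With no true effect, within-scale correlation 0.5 and between-scale correlation 0 / 0.5 / 0.8 (20,000 simulated trials, three visits per scale), at least one of eight contrasts falls below 5% in 32.4 / 27.5 / 20.7% of trials. For four omnibus tests the figure is 18.6 / 15.9 / 12.2%.

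**The case against.** The strongest reply is that 5.1.4 does ask for T0 comparisons. The method clause is attached to wording that names visits against T0, so the natural reading may be contrasts within the model. Contrasts and intervals for secondary changes are also commonly left to a separate analysis plan, which may exist. On the ANOVA branch much of this stands: the contrasts are available and the text arguably implies them. It does not carry over to the Friedman branch, where the named test has no T0 contrast or estimate to supply. Nor is the point only one of missing detail, because 5.1.4 does fix a method, and an analysis plan that followed it literally would carry the mismatch forward.

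A reader might infer that the precision of the change from T0 cannot be recovered from the planned analyses. The documents do not support that for the ANOVA branch, as the half-widths show. Section 5.1.2 also applies its summaries to all data and does not exclude summaries of change.

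A reader might also infer that the sponsor means to claim persistence at T16 from a global p-value. The protocol says nothing of the kind, and the T16 summaries will be on view. A multiplicity error cannot be alleged either, since no alpha is set for the secondary endpoints. Testing globally before visit contrasts is a defensible order, so whether to demote the omnibus test or to adjust the contrasts is a matter of choice.

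Finally, this is a single-arm pilot. Even a clear T16−T0 change would not by itself attribute the benefit to the device.

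**Conclusion.** The point holds in a limited form. Section 5.1.4 frames eight comparisons with T0 and fixes an omnibus method that does not by itself answer them. On the ANOVA branch this is a matter of asking explicitly for what the model can already give. On the Friedman branch it is a real gap, with neither a T0 comparison nor an estimate of change.

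The practical consequence is that a significant omnibus result carries no reliable information about T16. The size of the effect rests on the assumed sample, fall, correlations and normal data. The principle, that an early visit alone can drive the result, does not depend on those values. The impact is modest: secondary endpoints of a single-arm pilot only. It is worth correcting because the change is small and T16 is the protocol's only evidence on durability.

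**What to change.** Replace the method clause in 5.1.4 with text to this effect:

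*For VAS (T3, T16) and for DASH, FIHOA and pinch strength (T6, T16), the analysis is the change from T0 at the named visit with its 95% confidence interval. If the changes are roughly Gaussian, a model-based or paired contrast is used; otherwise the Wilcoxon signed-rank test with the Hodges-Lehmann median change and its interval. Repeated-measures ANOVA or the Friedman test may be reported alongside but supports no claim about a single visit. The eight contrasts are* [exploratory, without adjustment / adjusted for multiplicity by a named method].

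The bracketed choice is the sponsor's. The wording makes clear that all four scales are covered and keeps the protocol's own distribution-based choice of method.

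The cost is one clause and a little more analysis with standard software. Section 6.2 routes any change through the Ethics Committees as an amendment ("Qualsiasi modifica al presente Piano di Indagine sarà sottomessa dallo Sponsor, in forma di emendamento"), so it is best combined with other corrections. No new data are needed, and the primary endpoint and sample size stay as they are.

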6 ETHICAL REQUIREMENTS

6.1 Ethical Authorizations

Il Piano di Indagine Clinica sarà sottomesso ai Comitati Etici Territoriali di riferimento dei Centri di Indagine Clinica per l'espressione di parere.

6.2 Amendments to the Clinical Investigation Plan

Qualsiasi modifica al presente Piano di Indagine sarà sottomessa dallo Sponsor, in forma di emendamento, ai Comitati Etici Territoriali di riferimento dei Centri Sperimentali per opportuna approvazione.

6.3 Subject Information

The purposes and methods of the Investigation will be explained to each subject through an informative document (Informed Consent), containing what has been verbally explained by the clinician. The subject must personally date and sign the consent document.

A copy of the document will be provided to the subject while the original will be kept by the investigator.

No activity related to the Clinical Investigation can commence before the subject signs the Informed Consent.

6.4 Adverse Events

An Adverse Event is defined as any harmful clinical event that occurs during the Clinical Investigation in one of the subjects participating in the study population who has undergone the treatment specified by the Investigation Plan.

Adverse events will be classified as serious (SAE) or non-serious (AE).

An Adverse Event is defined as serious if (ICH-GCP DM 15/07/1997):

- it results in the death of the subject involved in the Investigation;
- it places the subject's life in jeopardy;
- it requires hospitalization;
- it requires prolonged hospitalization;
- it results in permanent or temporary disability;
- it results in a congenital anomaly or birth defect.

In all other cases, the Adverse Event will be non-serious and will be classified as:

- *mild*: does not interfere with normal daily activities and resolves spontaneously;
- *moderate*: interferes with daily activities but resolves spontaneously;
- *serious*: prevents daily activities and does not resolve spontaneously.

All personnel participating in the study who come into contact with enrolled subjects must report Adverse Events communicated by the subjects to the Principal Investigator, who is responsible for collecting all possible data regarding them.

Per Evento Avverso si intende qualsiasi evento clinico dannoso che si manifesterà nel corso dell'Indagine Clinica in uno dei soggetti che compongono la popolazione in studio che è stato sottoposto al trattamento previsto dal Piano di Indagine.

Gli eventi avversi saranno classificati in serio (SAE) non-serio (AE).

Un Evento Avverso viene definito serio se (ICH-GCP DM 15/07/1997):

- provoca il decesso del soggetto coinvolto nell'Indagine;
- pone il soggetto in pericolo di vita;
- è tale da richiedere il ricovero in ospedale;
- è tale da richiedere il prolungamento del ricovero ospedaliero;
- è tale da provocare un'invalidità permanente o momentanea;
- porta ad un'anomalia congenita o ad un difetto alla nascita.

In tutti gli altri casi l'Evento Avverso sarà non-serio e verrà classificato in:

- *lieve* non interferisce con le normali attività di vita quotidiane e si risolve spontaneamente;
- *moderato*, interferisce con le attività di vita quotidiane ma si risolve spontaneamente;

- *grave*, impedisce le attività di vita quotidiane e non si risolve spontaneamente.

Tutto il personale, partecipante allo studio, che viene a contatto con i soggetti arruolati deve riferire gli Eventi Avversi comunicati dagli stessi al Principal Investigator, il quale ha il dovere di raccogliere tutti i dati possibili in merito.

All Adverse Events (AE) must be reported by the Principal Investigator to the Guna S.p.a Clinical Research Unit within 24 hours through telephone, email, specific form, and simultaneously through the e-CRF. AE must also be reported to the Pharmacovigilance Office of Guna S.p.a.

Serious Adverse Events (SAE) must be reported to the Guna S.p.a Clinical Research Unit immediately (within 24 hours at most) by the Principal Investigator through telephone, email, specific form, and simultaneously through e-CRF. SAE must also be reported to the Pharmacovigilance Office of Guna S.p.a. These events will be promptly communicated to the Ethics Committee and the Ministry of Health.

Guna S.p.a Clinical Research Unit:

[contact]

mail:

[contact]

[contact]

[contact]

Guna S.p.a Pharmacovigilance Office:

[contact]

mail:

[contact]

[contact]

The Principal Investigator must implement all procedures to ensure the resolution of the event. In the case of Adverse Events (AE), it is necessary to consider that these may still give rise to Serious Adverse Events (SAE), which is why every Adverse Event must be monitored. Adverse Events not resolved at the end of the study will be followed up by the Investigators; every subject who has experienced an Adverse Event will be contacted at least once a month after the conclusion of the study for a number of months deemed appropriate.

6.5 Privacy Protection

The identities of the individuals involved will be known only to the Investigators and the Clinical Monitor responsible for monitoring the Investigation. Reference will be made to Regulation (EU) 2017/745.

Full respect for the anonymity of the subjects participating in the Investigation will be ensured. Data collection, processing, any scientific publications, or presentations at congresses of the results of the Clinical Investigation will be conducted in accordance with the current privacy regulations – Regulation (EU) 2016/679.

6.6 Data Access

In compliance with the current regulations regarding Clinical Investigations on medical devices [Regulation (EU) 2017/745] and the Good Clinical Practice Guidelines (ICH/GCP), the Clinical Investigation Centers and Investigators will allow monitoring of the study according to the monitoring plan developed by the Sponsor. Furthermore, they will allow the Competent Authorities direct access to the documentation related to the study during audits.

6.7 Data Ownership

All collected data will belong to Guna S.p.a. Milano, Italy, the Sponsor of the Clinical Investigation. Further information regarding data ownership is provided in the Contract.

6.8 Data Processing and Publication

The results of this study will be summarized and presented in a final report aimed at drawing reliable conclusions regarding the performance of the injectable medical device MD-Small Joints Collagen Medical Device in the treatment of trapeziometacarpal osteoarthritis. The scientific article will then be drafted and submitted to a peer-reviewed journal in the field for publication to disseminate the obtained results to the scientific community.

6.9 Financing

This research is funded by Guna S.p.a.

For further information, please refer to the Contract.

6.10 Reference Ethical Code

Reference is made to the Helsinki Declaration (Fortaleza 64th 2013), and the principles of Good Clinical Practice (GCP) (Legislative Decree 24 June 2003 – no.211 in G.U. no.184 of 09/08/2003) will be followed.

6.11 Subject Insurance

For the entire duration of the Investigation project, insurance coverage will be provided by Guna S.p.a. for all enrolled subjects.

7 PREMATURE INTERRUPTION OF THE INVESTIGATION

The Principal Investigators, reserve the right to prematurely terminate the Clinical Investigation at any time for reasonable medical and/or administrative reasons. The reasons for the interruption will be documented, and the Ethics Committees and the Ministry of Health will be informed of the decision.

8 TRIAL REGISTRATION

Guna S.p.a., Sponsor of the Clinical Investigation, will register the study on the Clinicaltrials.gov portal.

9 GLOSSARY

Medical device: any instrument, apparatus, implant, substance, or other article, whether used alone or in combination, including software, intended by the manufacturer to be used on humans for the purpose of diagnosis, prevention, monitoring, treatment, or alleviation of disease; diagnosis, monitoring, treatment, alleviation, or compensation for injury or disability; investigation, replacement, or modification of the anatomy or of a physiological process; intervention in conception, which does not achieve its principal intended action by pharmacological, immunological, or metabolic means, but which may be assisted in its function by such means.

10 ANNEXES TO THE INVESTIGATION PLAN

- A. Informed Consent (information and consent)
- B. Consent for the processing of personal data (information and consent)
- C. Clinical Diary
- D. Visual Analogue Scale (VAS)
- E. Disability of the Arm, Shoulder and Hand (DASH)
- F. Functional Index for Hand OsteoArthritis (FIHOA)

